1 INTRODUCTION

1.1 Background and Rationale

Allogeneic hematopoietic stem cell transplantation (alloSCT) is used to treat hematologic malignancies and other nonmalignant hematologic diseases and is a potentially curative treatment option. One of the major barriers to a successful transplant outcome is graft versus host disease (GVHD), which develops in 50–70% of patients who undergo alloSCT. Graft versus host disease is an inflammatory disorder which leads to tissue damage and ultimately organ failure and is categorized as either acute GVHD (aGVHD) or chronic GVHD (cGVHD).

Acute GVHD is most frequent within the first 100 days after transplantation and is the leading cause of non-relapse mortality (NRM) following alloSCT. Acute GVHD most typically affects the skin, gastrointestinal (GI) tract, and liver, and organ damage is characterized by apoptosis of cells.

Acute GVHD of the skin is generally not life-threatening, as both systemic and topical therapies are usually effective. While the incidence of Stage 3–4 liver GVHD is low (approximately 2%), the incidence of GI-aGVHD is reported to be between 40–50%. Treatment of GI-aGVHD remains unsuccessful in most cases, and the GI tract is involved in virtually all fatal cases of aGVHD.

Two distinct phenotypes of GI GVHD can be identified, upper GI (limited to Stage 1) and lower GI that differ in presentation, natural history, response to therapy, and risk of mortality. The upper GI phenotype generally does not progress to the lower GI phenotype. The upper GI phenotype presents with persistent loss of appetite, satiety, nausea, vomiting, and weight loss, with variable amounts of diarrhea, usually less than 500 mL per day. The presentation can be indolent, and therapy with prednisone at doses of 1 mg/kg/day plus topical oral corticosteroid is effective.

The lower GI phenotype of GVHD presents with secretory, protein-rich diarrhea and abdominal pain resulting from GI distention. In severe cases, the entire small intestine and colon are edematous and inflamed, with diarrheal volumes in excess of 1.5 L per day and evidence of mucosal ulceration and bleeding. Most patients with severe lower GI-aGVHD require prolonged hospitalization for supportive care including total parenteral support and pain control. Although outcomes are typically poor, the standard for initial therapy is prednisone, with the addition of other immune suppressive therapies when treatment with prednisone fails to control the disease.

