3.2 Eligibility Criteria

3.2.1 Inclusion Criteria

1. Signed informed consent for this trial prior to any trial specific assessment. A signed assent form will also be required for all subjects under the age of 18 years
2. Male or female subjects aged 12 years or above at the time of consent and who weigh a minimum of 40.0 kg. Only subjects aged 18 years and above will be included **in Germany and France**
3. Have undergone alloSCT from any donor source (matched unrelated donor, sibling, haplo-identical) using bone marrow, peripheral blood stem cells, or cord blood. Recipients of non-myeloablative, myeloablative, and reduced intensity conditioning are eligible
4. Evident myeloid and platelet engraftment confirmed prior to trial medication start:
 - a. Absolute neutrophil count $>1000/\text{mm}^3$
and
 - b. Platelets $\geq20,000/\text{mm}^3$
5. Use of growth factor supplementation (granulocyte-colony stimulating factor and granulocyte-macrophage-colony stimulating factor) and transfusion support is allowed
6. Clinical diagnosis of lower GI-aGVHD, **MAGIC Stage 1–4** prior to randomization. Suitable diagnostic procedures should be implemented to exclude alternative reasons for diarrhea; these include (but not limited to) fecal cultures and lower gut biopsy with histological assessment for infectious diseases
6. Clinically confirmed SR lower GI-aGVHD defined as subjects administered SS, given alone, or combined with CNIs and either:
 - a. Disease progression based on organ assessment after 3 days of systemic MP $\geq2 \text{ mg/kg/day}^3$ ([or prednisone dose $\geq2.5 \text{ mg/kg/day}$] or equivalent) \pm CNIs

³ The SS dose should be calculated based on the subject's actual weight, within the maximum lower margin of 15% from the calculated dose

or

b. Did not improve after 7 days of treatment with systemic MP ≥ 2 mg/kg/day³ ([or prednisone dose ≥ 2.5 mg/kg/day] or equivalent)

or

c. Progressed to a new organ after treatment with systemic MP ≥ 2 mg/kg/day³ ([or prednisone dose ≥ 2.5 mg/kg/day] or equivalent) for skin and upper GI-aGVHD

or

d. Recurred during or after a steroid taper. Initial dose should be ≥ 2 mg/kg/day³ MP (or equivalent) systemic MP ([or prednisone dose ≥ 2.5 mg/kg/day] or equivalent)

7. Treatment with SS plus RUX (RUX started concomitantly to apaglutide or a maximum of 72 hours before apaglutide initiation)

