7.8.2 Other Secondary Endpoints

Secondary endpoints will be summarized descriptively in the FAS. These endpoints are listed in Section 1.5.2.2.

Secondary endpoints assessed as binary responses will be summarized and analyzed in the same fashion as outlined above; if prior data for BAT are not available for a given time point, then only the apaglutide data will be presented.

Subjects with missing data such that response cannot be determined will be included in the analyses as non-responders. Again, supportive analyses of the secondary endpoints will be performed based only on those subjects with non-missing secondary endpoint data consistent with a missing at random assumption.

Secondary endpoints assessed as time-to-event endpoints will be summarized using Kaplan-Meier analysis. The median time duration of response will be presented where possible, along with the range and the associated 90% confidence interval. For comparison to BAT where prior data exist on duration of response, the distribution duration of response will be modelled via the inverse gamma distribution and thus compared on a Bayesian basis.

Where there are competing risks, time to event data will also be summarized using cumulative incidence. For endpoints like graft failure and NRM, subjects who die prior to reaching either endpoint will be right censored at the time of death. For comparison to BAT where prior data exist, for example for FFS, the distribution of mean time to event will be modelled via the inverse gamma distribution and thus compared on a Bayesian basis. Similarly, the distribution of event rates will be modelled via a gamma distribution and compared on a Bayesian basis.

Further details of these analyses will be outlined in the SAP.

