## 4.2 Analysis Sets

### 4.2.1 Full Analysis Set

The Full Analysis Set (FAS) comprises all enrolled subjects (randomized and non-randomized). All efficacy estimations will be conducted using the FAS. All subjects will be analyzed according to the apraglutide planned dose (High Dose, Low Dose, Low Body Weight Dose) and in total (Total randomized, Total).

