#### 4.3.5 *Underlying Disease History*

Count and percentage of recorded underlying disease history (recorded in the MH2 form of the eCRF) and associated classifications will be summarized by counts and percentages of subjects as appropriate by apaglutide dose levels and in total based on the FAS.

The primary classification of underlying diseases from MH2 form of the eCRF categories are as follows:

- Malignant – leukemia/ Myelodysplastic syndrome (MDS), which includes:
  - Acute myelogenous leukemia (AML or ANLL)
  - Acute lymphoblastic leukemia (ALL)
  - Acute leukemia of ambiguous lineage and other myeloid neoplasms
  - Chronic myelogenous leukemia (CML)
  - Myelodysplastic syndrome (MDS)
  - Myeloproliferative neoplasms (MPN)
  - Other leukemias
- Malignant – lymphoproliferative, which includes :
  - Hodgkin lymphoma
  - Non-Hodgkin lymphoma
  - Multiple myeloma / plasma cell disorder
- Non-malignant, which includes :
  - Aplastic anemia
  - Inherited bone marrow failure syndromes
  - Hemoglobinopathies
  - Paroxysmal nocturnal hemoglobinuria (PNH)
  - Disorders of immune system
  - Inherited abnormalities of platelets

- Inherited disorders of metabolism
- Histiocytic disorders
- Other, which includes :
  - Solid tumor
  - Other

In addition, time from diagnosis to first dose (days) will also be summarized using descriptive statistics for the FAS.

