#### *4.3.9.11 Incidence of malignancy relapse up to 2 years post-first dose of apaglutide*

The malignancy relapse/progression time is defined as the time from the date of the first dose to the date of hematologic malignancy relapse/progression.

Hematologic malignancy relapse/progression will be identified by manual review of reported malignancies or relapses in the AE data against the Underlying disease history CRF by the medical team, and confirmed with Sponsor. The list of identified hematologic malignancy relapse/progression will be finalized prior to the data base lock both for the Primary and the EOT analysis.

The malignancy/relapse progression will be summarized using Kaplan-Meier estimator. The number and percentage of subjects experiencing an event, and subjects censored will be summarized by apaglutide dose levels and in total. The median time-to-event will be presented where possible, along with the range and the associated two-sided 95% Brookmeyer-Crowley confidence interval. The event-free rate with 95% CI using Greenwood's formula will be provided for selected time points (e.g., 1, 3, 6, 12 and 24 months).

Plots of the Kaplan-Meier estimate for the malignancy/relapse progression will be presented by apaglutide dose levels and in total.

Subject for which no malignancy/relapse progression event occurs will be right censored at their last follow-up visit.

Incidence of malignancy/relapse progression will be analyzed only for the EOT analysis.

*4.3.9.12 Overall Survival up to 2 years post-first dose of apaglutide*

The overall survival time is defined as the time from the date of the first dose to the date of death due to any cause.

The last date known to be alive for each individual subject may be determined using, but not limited to, the following dates recorded on the eCRF:

- AE start and stop dates
- Study treatment start and stop dates
- Sample collection date for laboratory assessments
- Dates of any performed visit
- Start and stop dates of concomitant medications

Subjects who are alive at the time of data cut-off will be right censored on the date the subject was last known to be alive.

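### The relapse analysis in SAP 4.3.9.11 keeps subjects in the risk set who have no hematologic malignancy and cannot have the event; the at-risk set should be defined, and death treated as a competing event

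*SAP*

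**What the plan says.** **Endpoint and estimator.** SAP 4.3.9.11 defines the relapse endpoint as the "time from the date of the first dose to the date of hematologic malignancy relapse/progression". It is summarized by Kaplan-Meier, by dose level and in total, at the EOT analysis only. The censoring rule is that "Subject for which no malignancy/relapse progression event occurs will be right censored at their last follow-up visit".

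**Analysis set.** The section names none, so the general rules apply. SAP 4.2.1 says "All efficacy estimations will be conducted using the FAS", and protocol 7.8.2 says "Secondary endpoints will be summarized descriptively in the FAS". Under SAP 4.1, percentages also default to the size of the analysis set.

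**Who can be enrolled.** Inclusion criterion 3 (protocol 3.2.1) reads "Have undergone alloSCT from any donor source (matched unrelated donor, sibling, haplo-identical) using bone marrow, peripheral blood stem cells, or cord blood". No criterion requires a malignant indication; exclusions 3 and 15 only remove malignancy that has already relapsed. Protocol 1.1 notes that the procedure "is used to treat hematologic malignancies and other nonmalignant hematologic diseases". SAP 4.3.5, which classifies underlying disease from the MH2 form, has a class headed "Non-malignant, which includes" aplastic anemia, hemoglobinopathies, immune disorders and similar conditions. Its 'Other' class includes solid tumor.

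**Competing risks.** Protocol 7.8.2 says that time-to-event data with competing risks will also be summarized by cumulative incidence. SAP 4.3.9.11 does not provide this, and SAP section 6 does not list its removal as a change.

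**The concern.** A subject transplanted for aplastic anemia has no hematologic malignancy to relapse. Under the censoring rule this subject stays in the Kaplan-Meier risk set until last follow-up and in the denominator of the event percentage. The result mixes two quantities: how often malignancy returns among those who have one, and what fraction of those enrolled have one. The first is what a reader will take a relapse incidence to mean.

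The SAP handles other endpoints differently. Duration of response (4.3.9.7 and 4.3.9.9) is defined only for subjects with a response. SAP 4.3.9.11 itself has the medical team compare AE data with the underlying disease form, but uses that form to identify events and not to decide who is at risk.

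At stake is the interpretability of a named secondary endpoint. No comparison with external best-available-therapy data is planned for the Primary Analysis and no formal dose comparison at all (SAP section 6, items 7 and 12), so readers will depend on the descriptive figures.

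**Working it through.** The documents state no relapse rate, no expected share of non-malignant cases and no precision target for this endpoint, so there is no plan figure to reproduce. Inputs from the documents are 30 randomized subjects (15 per dose) plus up to 4 low-body-weight subjects, and 2 years of follow-up. Assumed inputs are q, the 2-year incidence among subjects with a hematologic malignancy, and f, the share of the FAS without one.

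**1. Dilution.** With equal censoring in the two groups, the FAS estimate is q(1-f).

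| q | f = 0 | f = 5% | f = 10% | f = 20% | f = 30% |
|---|---|---|---|---|---|
| 20% | 20% | 19% | 18% | 16% | 14% |
| 30% | 30% | 28.5% | 27% | 24% | 21% |
| 40% | 40% | 38% | 36% | 32% | 28% |

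A simulated Kaplan-Meier at 24 months with q = 30% gave 30.2%, 26.9%, 23.8% and 21.0% for f = 0, 10%, 20% and 30%, which agrees with the formula.

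**2. Size against sampling error.** At q = 20% and n = 34, the standard error of a proportion is sqrt(0.2 × 0.8 / 34) = 0.069, about 7 points. The dilution is 2 points at f = 10% and 4 points at f = 20%.

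**3. Between doses.** If the arms of 15 differ by k never-at-risk subjects, the dose difference shifts by qk/15. With q = 20% and 2 versus 5 such subjects, 0.20 × 13/15 = 17.3% and 0.20 × 10/15 = 13.3%, a 4-point gap at identical risk. For two independent Binomial(15, f) counts, the chance of a difference of 3 or more is 12% at f = 10% and 25% at f = 20%. The standard error of the dose difference is sqrt(2 × 0.2 × 0.8 / 15) = 0.146, about 15 points.

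**4. Deaths without relapse.** Censoring them makes one minus Kaplan-Meier exceed the true incidence. Take constant hazards, a true 2-year relapse incidence of 20% and death without relapse of 30%:

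- total cumulative hazard: -ln(1 - 0.5) = 0.693
- relapse share: 0.693 × 0.2/0.5 = 0.277
- one minus Kaplan-Meier: 1 - exp(-0.277) = 24.2%

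**5. Both effects together.** If the death hazard is the same in subjects with and without a malignancy, the reported figure is 0.242 × (1-f): 21.8% at f = 10% and 19.4% at f = 20%, against a true 20%. The net error can take either sign.

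**The case against.** The case for leaving the section alone has four parts.

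- **The effect is conditional and small.** The documents do not give the enrolled disease mix. If no such subject was enrolled, the estimate is unchanged; if a few were, the shift is below the sampling error. This stands, and it limits the weight of the point.
- **Case mix is not hidden.** SAP 4.3.5 tabulates underlying disease by dose level and in total, so a reader can recompute the crude proportion on the malignant denominator. This is true of the crude proportion only. The Kaplan-Meier curve, event-free rates and confidence intervals cannot be recovered that way.
- **Incidence among all treated subjects is a coherent quantity,** and relapse is a component of failure-free survival on the same FAS. This is fair, and it is why the whole-FAS figure should be kept beside the restricted one.
- **The event definition is not uniform.** The protocol synopsis footnotes speak of hematologic disease relapse, whereas Appendix 16.2 and the SAP speak of hematologic malignancy. Under the synopsis wording, recurrence of a non-malignant blood disorder might count. The point holds for the SAP definition, and the wording needs reconciling.

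Three stronger readings are tempting, and the documents do not support them. A reader might infer that the relapse figure is biased toward reassurance; steps 4 and 5 show that the net direction is not established. A reader might infer that chance imbalance could create or hide a dose effect; a shift of about 4 points against a standard error of about 15, with no formal dose comparison planned, does not bear that out. The randomization plan is also an external document, so the absence of stratification by disease cannot be confirmed. Finally, a reader might treat relapse as the trial's test of whether a growth-promoting peptide accelerates malignancy. The documents place that concern in the AESIs for new malignancies and colorectal polyps, the neoplastic-growth AEPI (SAP 4.3.8.3) and the trial hold criteria (protocol 6.6.3).

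**Conclusion.** The point holds as a denominator error that applies whenever any subject without a hematologic malignancy is in the FAS. The plan then reports q(1-f) in place of q: at q = 20%, a loss of 2 points for f = 10% and 4 points for f = 20%, and none for f = 0. This rests on the SAP's malignancy-based event definition, on the FAS applying by default because 4.3.9.11 names no set, and on assumed values of f and q. Any distortion between doses is small against sampling error. The net bias of the reported figure is uncertain, because the same section censors deaths without relapse and omits the cumulative incidence stated in protocol 7.8.2. The change is modest and worth making, since the analysis is run only at EOT and the MH2 disease classification is already collected.

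**What to change.** In SAP 4.3.9.11, before the EOT lock:

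1. Define the risk set as FAS subjects whose MH2 underlying disease is a hematologic malignancy. Classify each 'Other' entry in advance.
2. Show that n by dose level and in total.
3. Report cumulative incidence of relapse with death without relapse as a competing event, in line with protocol 7.8.2.
4. Keep the whole-FAS figure as supportive, and leave OS, FFS and NRM on the FAS.
5. Reconcile 'hematologic disease' in the protocol synopsis footnotes with 'hematologic malignancy' in protocol Appendix 16.2 and the SAP.

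The cost is a short SAP revision, a filter on an existing eCRF field, a brief review of the 'Other' entries and one further estimator. The number analysed falls slightly, and relapse no longer shares its main denominator with FFS and NRM; the supportive whole-FAS figure covers that.

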	
dose. Supportive safety analyses will be carried out on the SAS2 according to the dose of apaglutide received.
 
Analysis of Secondary Endpoints
 
Day 56 lower GI-aGVHD responses will be summarized and analyzed formally using Bayesian methods. In the Bayesian analyses, the response rates will be modelled by Beta distributions presenting the mean of the Beta distributions-associated with 90% credible intervals. The differences in response rates will be taken as the difference in mean response rates of the distributions on apaglutide with respect to BAT. The associated 90% credible interval will be computed using simulations of the respective distributions.
 
Secondary endpoints measured as response/non-response will be analyzed in the same fashion as described above. If prior data for BAT is not available for a given time point, then only the apaglutide data will be presented.
 
Secondary endpoints measured as time-to-event will be summarized using Kaplan-Meier analysis. Where there are competing risks, time-to-event data will also be summarized using cumulative incidence. The median time-to-event will be presented where possible, along with the associated 90% confidence interval. For comparison to BAT where prior data exist, the distribution of time-to-event will be modelled via the inverse gamma distribution, and thus compared on a Bayesian basis.
 
Secondary endpoints will be summarized descriptively in the LBW Analysis Set.
 
Exploratory Endpoints
 
These endpoints will also be summarized descriptively in both the FAS and the LBW Analysis Sets.
 
Analysis of Safety Endpoints
 
All safety data will be summarized by apaglutide dose level for both SAS1 and SAS2.
 
Adverse Events
 
All AESIs, treatment-emergent AEs (TEAEs), serious AEs, AEs leading to discontinuation, AEs leading to death, and laboratory abnormalities will be summarized by apaglutide dose level, severity, and relationship to treatment. Adverse event data will be coded using the Medical Dictionary for Regulatory Activities (MedDRA) and presented by SOC and Preferred Term (PT).

--	---

TMP no.: TMP-CD-04_1
Version no.: 1.0
TMP effective date: 10-Oct-2019

Proof-of-concept trial of apaglutide in GVHD

[figure not shown]

Good Clinical Practice statement:

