The overall survival time will be summarized using Kaplan-Meier estimator. The number and percentage of subjects experiencing an event (death), and subjects censored will be summarized by apaglutide dose levels and in total. The median time-to-event will be presented where possible, along with the range and the associated two-sided 95% Brookmeyer-Crowley confidence interval.

Plots of the Kaplan-Meier estimate for the overall survival will be presented by apaglutide dose levels and in total.

Overall Survival will be analyzed only for the EOT analysis.

*4.3.9.13 Non-relapse Mortality up to 2 years post-first dose of apaglutide*

The non-relapse mortality time is defined as the time from the date of the first dose to the date of death not preceded by hematologic malignancy relapse/progression.

The non-relapse mortality will be summarized using Kaplan-Meier estimator. The number and percentage of subjects experiencing an event, and subjects censored will be summarized by apaglutide dose levels and in total. The median time-to-event will be presented where possible, along with the range and the associated two-sided 95% Brookmeyer-Crowley confidence interval. The event-free rate with 95% CI using Greenwood's formula will be provided for selected time points (e.g., 1, 3, 6, 12 and 24 months).

Plots of the Kaplan-Meier estimate for the non-relapse mortality will be presented by apraglutide dose levels and in total.

Subject for which “hematologic malignancy relapse/progression” event occurs will be right censored at the time of occurrence of the event.

Subject for which neither “death” or “hematologic malignancy relapse/progression” event occurs will be right censored at their last follow-up visit.

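### The SAP drops the protocol's cumulative-incidence summary for NRM, relapse and graft failure without recording it, appears to transpose the infection and sepsis definitions, and times graft failure from transplant

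*SAP*

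**What the plan says.** **Competing risks.** Protocol 7.8.2 commits to Kaplan-Meier analysis of time-to-event endpoints and adds: "Where there are competing risks, time to event data will also be summarized using cumulative incidence". The synopsis makes the same commitment: "Where there are competing risks, time-to-event data will also be summarized using cumulative incidence". Protocol 7.8.2 then continues: "For endpoints like graft failure and NRM, subjects who die prior to reaching either endpoint will be right censored at the time of death".

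The SAP plans Kaplan-Meier only.
- NRM (4.3.9.13): "The non-relapse mortality will be summarized using Kaplan-Meier estimator". A subject in whom the relapse or progression "event occurs will be right censored at the time of occurrence of the event".
- Relapse (4.3.9.11): "The malignancy/relapse progression will be summarized using Kaplan-Meier estimator". The censoring rule is "Subject for which no malignancy/relapse progression event occurs will be right censored at their last follow-up visit", which by default takes in deaths without relapse.
- Graft failure (4.3.9.16): Kaplan-Meier, with a censoring rule only for subjects alive at cut-off.

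Each of these sections also tabulates the number and percentage of subjects with an event, the median, and event-free rates at selected times, for which 1, 3, 6, 12 and 24 months are given as examples. None of the 12 changes listed in SAP Section 6 mentions cumulative incidence.

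**Infections and sepsis.** SAP 4.3.9.17 derives both programmatically from Table 4-4. As extracted, that table puts SMQ 20000234 (Sepsis) in the infections row and the SOC Infections and Infestations in the sepsis row.

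**Graft-failure clock.** SAP 3.2 and the heading of 4.3.9.16 define the endpoint over the two years after first dose, but 4.3.9.16 measures time from transplant. The related endpoints start at dosing; for NRM, "The non-relapse mortality time is defined as the time from the date of the first dose". Inclusion criterion 4 requires confirmed engraftment before trial medication starts.

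**The concern.** Relapse and death without relapse compete, as do graft failure and death. When the competing event is censored, the Kaplan-Meier complement estimates risk as if the competing event did not exist, which exceeds the proportion of subjects who actually have the event. The protocol's additional summary would show the latter, and the SAP neither plans it nor says it was removed.

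The other two faults concern what the outputs would mean. Coded as the extracted table reads, every infection would be reported as sepsis, and only Sepsis-SMQ terms as infections. For graft failure, the transplant clock credits each subject with time before first dose that is event-free by selection, and no delayed entry is planned. The landmark rates therefore do not describe risk after dosing and do not line up with those for NRM, failure-free survival and relapse.

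**Working it through.** The documents give no NRM, relapse, graft-failure or infection rates and no transplant-to-dose gap, so there is no planned figure to reproduce. All rates and gaps below are assumptions.

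**1. Size of the competing-risk error.** Assume constant cause-specific hazards. For true 24-month incidences C1 and C2, the total cumulative hazard is H = −ln(1 − C1 − C2), with H1 = H × C1/(C1 + C2). True incidence of cause 1 at month t is (C1/(C1 + C2)) × (1 − exp(−H t/24)). The Kaplan-Meier complement (1 − KM) is 1 − exp(−H1 t/24).

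With 45% NRM and 15% relapse: H = −ln(0.40) = 0.916, so H1 = 0.687 and H2 = 0.229. The complements at 24 months are 1 − exp(−0.687) = 49.7% and 1 − exp(−0.229) = 20.5%.

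| Assumed true NRM / relapse, 24 months | 1 − KM, NRM / relapse |
|---|---|
| 35% / 10% | 37.2% / 12.4% |
| 45% / 15% | 49.7% / 20.5% |
| 50% / 20% | 57.7% / 29.1% |

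NRM over time in the 45%/15% case:

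| Month | True incidence | 1 − KM | Excess (points) |
|---|---|---|---|
| 3 | 8.1% | 8.2% | 0.1 |
| 6 | 15.4% | 15.8% | 0.4 |
| 12 | 27.6% | 29.1% | 1.5 |
| 24 | 45.0% | 49.7% | 4.7 |

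In 20,000 simulated trials of 34 subjects with complete 24-month follow-up (45%/15%), the standard deviation of 1 − KM is 9.2 points for NRM and 8.4 for relapse. The 24-month excesses of 4.7 and 5.5 points are systematic but smaller than that.

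For graft failure timed from first dose with deaths censored, a true 10.0% at 24 months gives 11.2%, 12.4% or 14.2% when 20%, 35% or 50% of subjects die without it.

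**2. NRM censoring date.** A death after relapse is not an NRM event. The protocol sentence censors such a subject at death; the SAP censors at relapse. The same subjects are censored under both rules, at different dates, and Section 6 does not note the difference.

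**3. Table 4-4.** No rate is needed to see that the labels exchange. If, say, 50–80% of subjects had an infection and 10–25% had sepsis, the output would print sepsis at 50–80% and infections at 10–25%.

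**4. Graft-failure clock.** Let the transplant-to-first-dose gap g be uniform on 1–4 months.
- At a 3-month landmark, P(g ≥ 3) = 1/3 of subjects are not yet dosed. Averaged over everyone, time since dose is E[max(3 − g, 0)] = 0.67 months, so among those already dosed it is 0.67/0.67 = 1.0 month.
- At the 24-month landmark the average time since dose is 24 − 2.5 = 21.5 months.
- Two years after first dose falls at months 25–28 of the transplant clock.

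With a gap of 2–6 months, 75% are undosed at 3 months, those dosed average 0.125/0.25 = 0.5 months, and the 24-month landmark averages 24 − 4 = 20.0 months after dose.

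**The case against.** The best defence is that little would be misread. These are descriptive secondary endpoints in an estimation-focused trial. SAP Section 6 states that comparison with external control data is not planned for the Primary Analysis and that no formal dose comparison will be made. The crude percentage with an event is already tabulated and equals cumulative incidence when follow-up is complete. Relapse and graft failure are analysed only at the end-of-trial step; only NRM is also in the Primary Analysis, where follow-up is shorter and the error smaller. Protocol 7.9 allows deviations to be reported in the trial report. All of that stands and limits the size of the point. It does not supply the promised summary when subjects withdraw or are lost, and it does not touch the table or the clock.

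A reader might infer more than the documents support:
- That Kaplan-Meier is itself contrary to the protocol. It is not; the protocol asks for cumulative incidence in addition.
- That the protocol's rule of censoring NRM at death is impossible. It is loose but coherent when read as covering deaths after relapse.
- That the SAP will print inflated incidences, or NRM and relapse figures that add up to too much. It prints event-free rates; a reader would have to form the complements and the sum.
- That graft-failure landmarks clash with those of overall survival. SAP 4.3.9.12 plans no landmark rates for survival, and the listed time points are only examples.
- That the 1-month graft-failure rate must be 100% event-free. That needs a minimum gap of one month, which the documents do not state.
- That Table 4-4 is certainly wrong in print. The extracted table has no header row and extraction can fail; the PDF must be checked. Programming specifications are also held in a separate document.

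**Conclusion.** The point holds with modest impact and should be fixed. Omitting cumulative incidence is an unrecorded departure from a commitment made twice in the protocol. Across the assumed scenarios the Kaplan-Meier complement overstates 24-month NRM by about 2 to 8 points and relapse by about 2 to 9. These sizes rest on constant hazards and assumed event rates. If the PDF matches the extracted text, Table 4-4 would make the infection and sepsis output wrong whatever the data show. The graft-failure clock is inconsistent with the endpoint's own definition; how far its landmarks shift depends on the transplant-to-dose gap. The SAP also gives no rule for deaths without graft failure; only the protocol does. The primary safety objective, the general SOC/PT tables and the Day 56 response are not affected.

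**What to change.** 1. Add Aalen-Johansen cumulative incidence beside the Kaplan-Meier output in SAP 4.3.9.11, 4.3.9.13 and 4.3.9.16: relapse competing with NRM, non-relapse death with relapse, and death with graft failure.
2. State in SAP Section 6 that NRM is censored at relapse, whereas Protocol 7.8.2 censors deaths that are not NRM events at the date of death.
3. Check Table 4-4 against the PDF and, if it reads as extracted, swap the two rows.
4. Start graft-failure time at first dose, or keep the transplant clock with delayed entry at first dose, and state how deaths without graft failure are handled.
5. Record any remaining departure from Protocol 7.8.2 in Section 6.

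The cost is SAP wording and minor programming. No new data are needed: time from transplant to randomization is already derived under SAP 4.3.4, and the NRM and relapse Kaplan-Meier outputs stay as they are.
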